# Table 1 Clinical Assessment Schedule

- 1. Permissible range for clinical assessments: After Day 1 (except for the follow-up and discontinuation tests), clinical assessments will be performed as specified in Section 5.1.10. The permissible range for the 2nd (Week 12) and 3rd hospitalization (Week 24) will be the standard hospitalization day ± 7 days. For hospitalization on any day other than the standard hospitalization day, pooled urine will also be started on the day after hospitalization, and the efficacy evaluation including that of motor function (hereinafter referred to as the efficacy evaluation), will be performed on the end day of pooled urine. However, if the efficacy evaluation cannot be performed on the end day of pooled urine to an adverse event or any other reason, the efficacy evaluation may be performed within the end day of pooled urine + 2 days (this permissible range for the efficacy evaluation will also apply to the baseline evaluation). The increase in the number of hospitalization day at ue to the delay of the efficacy evaluation (excluding prolonged hospitalization due to inpatient treatment) will not be assessed as a serious adverse event. For hospitalization within the permissible range of standard hospitalization day at Week 24 (Day 167) ± 7 days (Day 160 to Day 174), the investigational product will not be administered after the efficacy evaluation.
- 2. Subject ID code entry: A unique subject ID code will be provided to each patient whose legal representative has received an explanation of informed consent (the patient should also receive an explanation of informed consent/assent whenever possible).
- 3. Body weight: No dose increase/decrease will be considered according to body weight increase/decrease during the study.
- 4. Hospitalization: In principle, the duration of the initial hospitalization (Day -2 to Day 6) will be 8 days and 7 nights. In principle, the discharge day for the 2nd hospitalization (hospitalized on Day 83 and discharged on Day 85) and the 3rd hospitalization (hospitalized on Day 167 and discharged on Day 169) will be the day of the efficacy evaluation; however, subjects who visit the site from afar may be discharged on the day after the efficacy evaluation. Subjects will be appropriately instructed before hospitalization to bring all the prescribed investigational products (managed by their legal representatives) and subject medication diary at each hospitalization.
- 5. Investigational product administration: The first dose will be administered after dinner on Day 1, and the last dose will be administered after breakfast on the efficacy evaluation day at Week 24. Any suspended or missed dose during the administration period will not be administered later than administration after breakfast on the efficacy evaluation day at Week 24. The investigational product will be additionally prescribed in accordance withTable 3.2-1.
- 6. Blood pressure, pulse rate, body temperature, hematology/biochemistry/endocrinology, and urinalysis: The subject will be kept at rest and fasted wherever possible for 3 to 4 hours (standard) before blood collection for laboratory tests. The measurement on the efficacy evaluation day will be performed before the evaluation. Blood pressure and pulse rate will be measured after the subject is confirmed to be at rest in a supine or sitting position for several minutes, and the measurement will be immediately repeated if any abnormality is observed. Since cortisol is subject to diurnal variation, the endocrinological parameters, including adrenocorticotropic hormone (ACTH), will be measured at 8:00 to 10:00 am (standard) only during the hospitalization period.
- 7. 12-lead ECG, cardiac ultrasonography (echocardiography): The measurement will be performed after the subject is confirmed to be at rest for several minutes. The measurement on the efficacy evaluation day will be performed before the evaluation.
- 8. BIA, lean body mass: The measurement will be performed using a body composition monitor (TANITA BC-622).
- 9. Urinary tetranor-PGDM and tetranor-PGEM concentrations, urinary creatinine and creatine concentrations, urine weight, and urine specific gravity: During the baseline and administration periods, urine will be pooled (under refrigeration) for approximately 24 hours from immediately after waking on Day 4 to immediately after waking on Day 5 (initiation of pooled urine within Day 4±1 day is permissible as shown in Section 5.1.10). For urinary tetranor-PGDM and tetranor-PGEM concentrations, frozen samples will be collected by an external contractor and analyzed at the Pharmacokinetics Research Laboratories of Taiho Pharmaceutical Co., Ltd. Urinary creatinine and creatine concentrations, urine weight, and urine specific gravity will be measured at the study site. Urine volume (mL) will be calculated from the measured urine weight (g) and urine specific gravity (g/mL) at the study site.
- 10. Subject medication diary: The subject and his legal representative will bring the subject medication diary at each visit and submit it during the medical examination. The subject medication diary will be collected at each visit for ongoing drug accountability check and appropriate instruction. If the subject medication diary is left behind at home, it may be collected at the subsequent visit. Drug accountability to facilitate additional prescription of the investigational product is described in Note 5, above.
- 11. Assessments of concomitant medication/therapy and adverse events: Investigated from the time of informed consent to the end of the follow-up period (follow-up or discontinuation test)
- 12. Data from any evaluation/test performed as specified within 14 days before enrollment can be used as screening data, even if obtained before informed consent.
- 13. Initial hospitalization: The subject will be hospitalized (on Day -2) within 12 days after enrollment.
- 14. Administration start day (Day 1): The administration of the investigational product will be started after dinner on the end day of pooled urine (within 14 days after enrollment); however, if it is not possible to perform the efficacy evaluation (corresponding to Note 1) due to an adverse event or any other reason, or to start the investigational product administration on the end day of pooled urine, the administration may be started after dinner within the end day of pooled urine + 2 days (within up to 16 days after enrollment) (the actual administration start day will be designated as Day 1). The increase in the number of hospitalization days due to the delay of the administration start day (excluding prolonged hospitalization due to inpatient treatment) will not be assessed as a serious adverse event.
- 15. Clinical assessments in the baseline period: Performed no later than administration on the investigational product administration start day (administration after dinner on Day 1), in principle
- 16. Discontinuation test: Performed at the first visit after discontinuation whenever possible (safety endpoints will be evaluated)
- 17. Efficacy endpoints on the end day of administration: Evaluated after the last dose of the investigational product (standard: administration after breakfast on Day 169)
- 18. Follow-up test: Performed 21 days after the last day of the investigational product administration (standard day ± 7 days is permissible).
- 19. Endocrinology at the follow-up test: Performed only if an abnormal change (adverse event) is observed in the test on the discharge day for the 3rd hospitalization (standard: Day 169). Such an endocrinological test will be performed around 8:00 to 10:00 am on the follow-up test day. For subjects who visit the study site from afar, a stay at night before the follow-up test day (stay at or outside the study site; planned hospitalization or stay at a nearby facility) will be considered to collect blood within the specified time window whenever possible.

# 1. Background Information

#### 1.1 Introduction

Duchenne Muscular Dystrophy (DMD) affects approximately 1 in 3500 male births worldwide, and the number of patients with DMD in Japan is estimated to be approximately 5000. DMD is caused by a mutation in the dystrophin gene resulting in the absence of dystrophin protein, which is normally located immediately beneath the muscle sarcolemma. The clinical course of DMD is characterized by maximal motor function between the ages of 4 and 5 years, followed by progressive muscle weakness and then loss of the ability to walk at approximately 10 years of age. The gene mutations include exon deletions, duplications, and micro mutations such as point mutations, which account for approximately 60%, 10%, and 30%, respectively.

While the cause of DMD is the lack of dystrophin protein due to a mutation in the dystrophin gene, the mechanism for development of DMD is not fully understood. It is suggested that immunity and inflammatory responses may be involved in the development of the disease. Prostaglandin  $D_2$  (PGD2) is one of the major prostaglandins involved in inflammation, and is produced from arachidonic acid, a cell membrane constituent, by phospholipase  $A_2$ , cyclooxygenase, and then prostaglandin D synthase. There are 2 types of prostaglandin D synthase: one is known as lipocalin-type and primarily located in the central nervous system and produces PGD2, which centrally acts via the prostaglandin D2 receptor 1 (DP1) to induce sleep, regulate pain response, etc.; and the other is hematopoietic prostaglandin D synthase, which is known to be primarily expressed in mast cells, type 2 T helper cells, and microglial calls.

For patients with DMD, no effective treatments are available except for oral steroids, but oral steroids require dose reduction, change in regimen, and even dose suspension in order to manage associated adverse reactions; therefore, a new treatment is highly needed. While no clinical studies to evaluate the efficacy of TAS-205 have been conducted in patients with allergic rhinitis, development of a new treatment for DMD is considered to be highly valuable, and thus a Phase I single- and repeated-dose study in patients with DMD was conducted. In this study, TAS-205 was demonstrated to be highly safe and tolerable in patients with DMD when given at 1.67 to 13.33 mg/kg as a single dose and at repeated doses twice daily for 7 days. TAS-205 also decreased urinary excretion of tetranor-PGDM (total excretion of tetranor-PGDM and tetranor-PGDM/Cre concentration ratio), a marker of PGD2 production, with increasing dose. Significantly increased urinary excretion of tetranor-PGDM in nonambulatory subjects compared with ambulatory subjects when analyzed by ambulatory function as the subject characteristic, as well as higher urinary excretion in patients with DMD aged 8 years or older compared with healthy subjects of the same age and reportedly increased urinary excretion with age suggest involvement of PGD2 production in the development of DMD. In conclusion, it was considered of great significance to evaluate the efficacy of TAS-205 in patients with DMD, and an early Phase II study in these patients was therefore planned.

#### 1.2 TAS-205

#### 1.2.1 Mechanism of Action

TAS-205 inhibits HPGDS selectively and competitively.

### 1.3 Overview of Risks and Benefits

#### 1.3.1 TAS-205

Since only Phase I studies have been conducted with TAS-205 to investigate the tolerability, pharmacokinetics, and pharmacodynamics in healthy adult male subjects and patients with DMD, and only

limited information is available on the efficacy, benefits of TAS-205 has not been confirmed yet at the initiation of the present study.

# 1.3.2 Risks and Benefits Expected in the Study

This study is expected to provide information on the efficacy of TAS-205 (high and low doses) for deterioration of physical function (motor function, muscle volume, and muscle strength) and the dose relationship of TAS-205 in patients with DMD. In addition, the study is expected to provide information on the long-term safety of TAS-205 administered twice daily for 24 consecutive weeks. Since no significant or potentially significant risks have been identified with TAS-205, no risks are expected in the present study; however, the high dose of TAS-205 has never been administered in clinical studies, and thus the tolerability of TAS-205 at the high dose has not been demonstrated yet at the initiation of the present study.

# 1.4 Major Study Results

# 1.4.1 Nonclinical Studies

Refer to the Investigator's Brochure DMD Ver. 3 (revised on March 24, 2016).

# 1.4.2 Clinical Studies

# 1.4.2.1 Study 10053010 (Phase I Study in Healthy Adult Subjects)

# 1.4.2.2 Study 10053030 (Phase I Study in Patients with DMD)

A Phase I single- and repeated-dose clinical study of TAS-205 was conducted in patients with DMD (hereinafter referred to as Study 10053030) to evaluate the safety and pharmacokinetics of TAS-205, as well as the effects of TAS-205 on urinary excretion of tetranor-PGDM and tetranor-PGEM in an exploratory manner after a single oral dose and repeated oral doses twice daily for 7 days (Steps 1 and A: 1.67 - 3.33 mg/kg/dose, Steps 2 and B: 3.33 - 6.67 mg/kg/dose, Steps 3 and C: 6.67 - 13.33 mg/kg/dose).

In the single dose period, a total of 15 subjects in the TAS-205 group, with 5 subjects per step, and a total of 6 subjects in the placebo group were treated with the investigational product. Pharmacokinetics was evaluated only in 15 subjects in the TAS-205 group. Pharmacodynamics was evaluated in 15 subjects in the TAS-205 group.

In the repeated dose period, a total of 14 subjects in the TAS-205 group (in Steps A to C) and a total of 5 subjects in the placebo group were treated with the investigational product. Pharmacokinetics was evaluated only in the 14 subjects in the TAS-205 group administered the investigational product, and all subjects in the placebo group were excluded from the pharmacokinetic evaluation. Pharmacodynamics was evaluated in the 14 subjects in the TAS-205 group and 5 subjects in the placebo group were treated with the investigational product.

The pharmacokinetics of TAS-205 was linear in the dose range studied and reached steady state after repeated doses for 4 days. In addition, it was suggested that TAS-205 decreased urinary excretion of tetranor-PGDM (total excretion of tetranor-PGDM and tetranor-PGDM/Cre concentration ratio) with increasing dose at each measurement time point, without affecting urinary excretion of tetranor-PGEM.

In the safety evaluation in this study, no deaths or other serious adverse events were reported in any subjects. No subjects were withdrawn from the study due to adverse events in any dosing period. In the TAS-205 group as compared with the placebo group, adverse events occurred, and adverse drug reactions also occurred in the single dose period, but not in the repeated dose period. None of the adverse events reported in the TAS-205 group were common to all steps or tended to increase dose-dependently in any dosing period; all adverse events were mild in severity and resolving or resolved. In addition, no clinically significant abnormal changes were observed in laboratory values, 12-lead ECG, blood pressure, or pulse rate. In the repeated dose period, an abnormal change in body temperature was observed in 1 subject in Step B in the TAS-205 group; however, this was associated with nasopharyngitis. Other measured values were comparable to those in the placebo group, with no clinically significant changes post-/pre-dose .

In conclusion, TAS-205 was demonstrated to be highly safe and tolerable in patients with DMD when given at 1.67 to 13.33 mg/kg/dose as a single oral dose and repeated oral doses twice daily for 7 days.

#### **1.5** Rationale for the Study and Study Population

#### **1.5.1** Study Population

This study is an early Phase II study to evaluate the efficacy of TAS-205 (low dose and high dose) administered orally twice daily for 24 consecutive weeks in patients with DMD. The study will also be conducted to evaluate the safety of TAS-205 as well as the relationship between the pharmacodynamic or exploratory endpoints and the efficacy in an exploratory manner. Since the efficacy for deterioration of physical function will be primarily evaluated, this study will include ambulatory patients with DMD aged 5 years or older who meet all of the inclusion criteria and none of the exclusion criteria.

#### 1.5.2 Study Design

# 1.5.3 Dosage of TAS-205

Since a marked increase in body weight during the 24-week evaluation period is unlikely and dose increase/decrease according to body weight increase/decrease during the study may be unnecessary based on the dose setting in 7.5-kg or 15-kg increments of body weight in the present study, the dose for each subject during the evaluation period will be fixed based on the body weight data in the screening period (within 14 days before enrollment). In summary, the subjects assigned to the active drug groups will receive the number of TAS-205 tablets per dose specified by the body weight measured within 14 days before enrollment, as shown in Table 7.1.1-1, orally twice daily, within 30 minutes after breakfast and dinner, for 24 consecutive weeks.

#### 1.5.4 Selection of TAS-205 Placebo

In this study, a placebo group will be included to evaluate the efficacy of TAS-205 for deterioration of physical function (e.g., motor function, muscle volume, muscle strength) after oral administration twice daily for 24 consecutive weeks as well as the safety after repeated administration for 24 weeks, in an appropriate and objective manner. In order to maintain blindness of the low-dose and high-dose groups, in which different numbers of TAS-205 50 mg tablets (active drug) will be administered, the subjects assigned to the low-dose group will receive the active drug tablets with the same number of placebo tablets. In summary, the subjects assigned to the placebo and the low-dose groups will receive the number of tablets per dose specified based on the body weight measured within 14 days before enrollment, as shown in Table 7.1.1-1, orally twice daily, within 30 minutes after breakfast and dinner, for 24 consecutive weeks. Since this study is designed to permit subjects who had been using steroid before informed consent to continue their steroid therapy as far as no changes are made to their dosage regimen after informed consent, inclusion of a placebo group is considered ethically acceptable.

# 2. Study Objectives

### 2.1 Primary Objective

To evaluate the efficacy of TAS-205 administered orally twice daily for 24 consecutive weeks compared with placebo in patients with DMD in an exploratory manner.

#### 2.2 Secondary Objective

To evaluate the safety and dose relationship of TAS-205 administered orally twice daily for 24 consecutive weeks compared with placebo in patients with DMD.

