### 3.2 Subject Randomization and Blinding

### 3.2.1 Randomization Method

This study is a randomized study.

After providing due explanation to each prospective patient and his legal representative, the investigator or subinvestigator will obtain written informed consent/assent, and then prepare a screening log of patients whose legal representative consented to participate in the study in order to check the patient enrollment in the study. After confirming that the prospective patient is deemed eligible by meeting all of the inclusion criteria and none of the exclusion criteria, all necessary information will be entered the Interactive Web Response System (IWRS) and submitted to the Enrollment Center.

Upon completion of enrollment after confirmation of subject eligibility, the subjects will be randomly assigned to the low-dose group, high-dose group, or placebo group in a ratio of 1:1:1 via IWRS based on a dynamic randomization method (minimization method).

Data will be entered in accordance with the description in the IWRS procedure.

The subjects will be stratified by the following randomization adjustment factors:

- Age (between 5 and 6 years, 7 years or older)
- Presence or absence of concomitant steroid use

The above-mentioned enrollment and randomization will be centrally managed; after completion of the enrollment procedure, each subject will be assigned to a treatment group and given an investigational product number to be initially prescribed (for 6-week administration) by the enrollment system.

The investigational product numbers corresponding to subject randomization will be given and reported to the study site with instructions on the investigational product prescription via IWRS. For more detailed information, refer to the IWRS procedure.

If an investigational product not corresponding to the number given via IWRS is prescribed to a subject in error, the IWRS help desk must be notified immediately. In addition, the cause of the erroneous prescription of the investigational product must be recorded at the study site. If a subject receives the investigational product for a different treatment group due to an error in the investigational product number allocation or prescription, the subject will continue to receive the investigational product for the rest of the study period.

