# 13.1.4 Target Sample Size and Rationale for the Sample Size

Target sample size: a total of 33 subjects (11 subjects for each group)

Given that DMD is a rare disease that allows only limited recruitment of subjects and that this study is primarily intended to evaluate the efficacy of TAS-205 in an exploratory manner, the sample size was determined not statistically, but based on feasibility.

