#### **6.1** Analysis of the Primary Endpoint

The following analyses will be performed in the PPS and FAS:

The following analyses will be performed for the primary endpoint, defined as the change from baseline in 6MWD at Week 24: Analysis will also be conducted in the group combining the low-dose group and the high-dose group excluding the analysis of MMRM.

- A 2-sample t-test will be performed between each treatment group and placebo group. This analysis will be performed with and without the LOCF imputation. Analyses will also be conducted with the following baseline definitions.
  - (1) Analysis excluding the subjects for whom the value of (6MWD on Day 1 6MWD at screening)/6MWD at screening is 0.2 or higher or -0.2 or lower
  - (2) Analysis using the mean value of 6MWD on Day 1 and 6MWD at screening as the baseline value
- With respect to the above analysis, subgroup analysis will be conducted for the following items.

Subgroup analysis: Presence or absence of the history of steroid use, age category ( $\geq$ 5 years and <7 years, and  $\geq$ 7 years), and baseline 6MWD (<350 m, and  $\geq$ 350 m)

- The treatment effect will be estimated using the MMRM. The changes from baseline in 6MWD measured at other time points will also be included in this analysis. Covariates will be the assigned group, baseline value, time point, and the interaction term of the assigned group and time point.
- Using the MMRM, the dose relationship will be analyzed with treatment contrasts of (placebo group, low-dose group, high-dose group) = (-2 1 1), (-1 0 1), and (-1 -1 2). The changes from baseline in 6MWD measured at other time points will also be included in this analysis. Covariates will be the assigned group, baseline value, time point, and the interaction term of the assigned group and time point.
- For the above 2 analyses, analyses will be conducted in the PPS by adding age and the presence or absence of the history of steroid use to explanatory variables. In addition, subgroup analysis will be conducted for the following items.

Subgroup analysis: Baseline 6MWD ( $\leq$ 350 m, and  $\geq$ 350 m)

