## **6.2.2** SAFETY ANALYSIS

The analyses described below will be performed in treated patients for each treatment group. In tabulation of adverse events (adverse drug reactions), System Organ Class (SOC) and Preferred terms (PT) of MedDRA will be used. An exact method based on F distribution will be used for estimation of the confidence interval of incidences.

The adverse events which have occurred or become exacerbated after administration of the investigational product will be tabulated.

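### Safety is to be evaluated compared with placebo, but the safety sections plan only per-arm summaries: no difference from placebo with its uncertainty, and no combined TAS-205 group, although efficacy and pharmacodynamics have both

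*Protocol*

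**What the plan says.** Protocol 2.2 gives the secondary objective as "To evaluate the safety and dose relationship of TAS-205 administered orally twice daily for 24 consecutive weeks compared with placebo in patients with DMD", and SAP 3.1 repeats it. Protocol 1.5.4 gives two reasons for a placebo group: efficacy, and "as well as the safety after repeated administration for 24 weeks, in an appropriate and objective manner". Protocol 1.3.2 adds that "the study is expected to provide information on the long-term safety of TAS-205 administered twice daily for 24 consecutive weeks". The same section notes that the high dose has not been given in any earlier clinical study.

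The safety analysis in SAP 6.2.2 opens with "The analyses described below will be performed in treated patients for each treatment group", and Protocol 13.1.3.3.2 is to the same effect. What follows is by arm: adverse event incidences by preferred term and severity, listings, summary statistics for laboratory values, vital signs, ECG and echocardiography, and QTcF categories. The intervals are exact limits for a single incidence (SAP 6.2.2 and 8.3).

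For the primary endpoint, SAP 6.1 says "Analysis will also be conducted in the group combining the low-dose group and the high-dose group excluding the analysis of MMRM". SAP 6.2.1 and 6.3 carry a similar sentence for the secondary efficacy endpoints and for the pharmacodynamic and exploratory endpoints. All three sections also plan two-sample t-tests against placebo and MMRM estimates and dose contrasts, which SAP 8.3 gives with 95% intervals.

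On size, Protocol 13.1.4 states "Target sample size: a total of 33 subjects (11 subjects for each group") and explains that "the sample size was determined not statistically, but based on feasibility". Subjects are "randomly assigned to the low-dose group, high-dose group, or placebo group in a ratio of 1:1:1".

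**The concern.** The objective is comparative, but in the safety sections the comparison is left to the reader's eye. Two incidences from arms of 11 can look far apart and still be compatible with no difference or with a large one. Separate intervals for each arm do not show this directly.

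The plan also gives no statement about TAS-205 as a whole. If an event is not seen on either dose, the planned display bounds its risk from 11 boys at a time, although 22 are to receive the drug. The SAP adopts pooling and placebo contrasts for every other class of endpoint and gives no reason for leaving safety out.

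**Working it through.** **Inputs.** Arm sizes come from Protocol 13.1.4: 33/3 = 11 per arm, consistent with 1:1:1 allocation, so 22 on TAS-205 if all 33 are treated. The two-sided 95% level and the exact method are those of SAP 8.3. The documents give no adverse event rates, so every rate below is an assumption. Because the sample size rests on feasibility, there is no power figure to reproduce.

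**1. Bound when no event is seen.** The exact upper limit for 0/n is 1 − 0.025^(1/n).
- n = 11: 1 − 0.025^(1/11) = 28.5%.
- n = 22: 1 − 0.025^(1/22) = 15.4%.

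**2. What an interval for the difference would show.** The Newcombe interval combines the Wilson limits (l, u) of the two proportions:
- lower = d − √[(p1 − l1)² + (u2 − p2)²]
- upper = d + √[(u1 − p1)² + (p2 − l2)²]

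Suppose 3/11 on one dose against 1/11 on placebo, so d = 18.2 points. The Wilson limits are 9.7% to 56.6% and 1.6% to 37.7%.
- Lower: 0.182 − √[(0.273 − 0.097)² + (0.377 − 0.091)²] = −15.4 points.
- Upper: 0.182 + √[(0.566 − 0.273)² + (0.091 − 0.016)²] = +48.4 points.

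At the same incidences with the doses combined (6/22 against 1/11), the interval is −13.8 to +40.4 points. The gain in precision is modest. With equal variances the standard error falls to √(1/22 + 1/11) / √(2/11) = 0.866 of its single-arm value.

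**3. How often the interval would exclude zero.** This is the exact enumeration of the probability that the Newcombe lower limit exceeds 0, with the same true rate at both doses:

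| Assumed TAS-205 v placebo | One dose (11 v 11) | Combined (22 v 11) |
|---|---|---|
| 40% v 5% | 49% | 61% |
| 30% v 10% | 17% | 20% |
| 20% v 5% | 10% | 8% |

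Combining helps when the harm is common and the contrast large. It does little, or slightly reverses, at lower rates.

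**4. Harm at one dose only.** Assume placebo 5%, low dose 5%, high dose 40%. The true high-dose difference is 35 points. The combined rate is (5% + 40%)/2 = 22.5%, so the pooled difference is 17.5 points. The interval excludes zero with probability 49% for high dose against placebo and 11% for the combined group.

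**The case against.** The strongest reply is that nothing is lost. Placebo is one of the tabulated arms, and per-arm counts and denominators let anyone form a difference, a pooled count or an exact bound on x/22. The trial is exploratory, and even its primary analysis (SAP 5) is per-arm summary statistics. Per-dose safety also has a good reason behind it: dose relationship is part of the same objective, and the high dose is untested, while the low-dose range matches the top step of the Phase I study in DMD (Protocol 1.4.2.2). All of this stands. It means the gap is in what is pre-specified and displayed, and that per-dose columns should lead. It does not explain why the exploratory efficacy analysis gets planned contrasts and a combined group and safety gets neither.

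Three stronger readings are tempting and are not supported.
- A reader might infer that the trial cannot compare safety with placebo at all. It can, informally; what is missing is a planned estimate with its uncertainty.
- A reader might infer that pooling makes a rare harm more likely to be seen. It does not. The same 22 boys are treated and all their adverse events are listed by subject (SAP 6.2.2) with or without a combined column. Nor does pooling reliably sharpen the contrast for less common harms, as step 3 shows.
- A reader might infer that no combined safety output exists anywhere. SAP 6 and 7 refer to an item list in the appendix, of which only Tables 10.1 and 10.2 are in the text available. The absence is established for SAP 6.2.2 and Protocol 13.1.3.3.2, not for that list.

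**Conclusion.** The concern holds as a gap between objective and analysis. The safety sections give a comparative objective no comparative estimate, and they depart without explanation from the SAP's practice for other endpoints. The firmest number is the zero-event bound: 28.5% from one arm against 15.4% from both, if all 33 are treated. The benefit for the placebo contrast depends on the scenario, from 49% rising to 61% at 40% v 5%, down to 10% falling to 8% at 20% v 5%, all on assumed rates and equal risk at both doses. The case for the change therefore rests mainly on showing the uncertainty of the stated comparison, and only partly on precision. The change should be made, but the gap does not undermine the trial, and no formal safety test is called for.

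**What to change.** In SAP 6.2.2:
- Keep the per-arm columns as the main display.
- Add a combined TAS-205 column, using the combined-group sentence already in 6.1, 6.2.1 and 6.3.
- For each dose and for the combined group, give the difference in incidence from placebo with a 95% interval (for example Newcombe), labelled descriptive.
- Apply this in items (1), (2), (4) and (6): any adverse event, adverse drug reactions, severe and serious events, events leading to suspension, reduction or discontinuation, and the ECG and echocardiography abnormality proportions.
- State that the combined contrast supplements the per-dose contrasts and does not replace them.

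If the appendix list already holds such outputs, a cross-reference in 6.2.2 would do for those.

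The cost is SAP wording and a few table columns, with no new data and no change to trial conduct. The downside is the dilution of harm confined to one dose shown in step 4, which is why the per-dose results must stay in front.
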